9.2. Concomitant Medications

Concomitant medications (other than prohibited concomitant medications listed in [Section 9.2.2](#)) will be used at the discretion of the usual care provider (or Investigator if also the usual care provider). Relevant information about all concomitant medications (including prescribed, over the-counter, or herbal preparations) taken within 30 days of Screening and during the study must be recorded in the source documents and eCRF, as well as any dose or dose regimen changes that occur during the study. Concomitant medications should be stable prior to Day 1.

PBC Specific Therapy

Investigators will be encouraged to follow guidelines for care based upon local and institutional practice patterns and any relevant published practice guidelines. Throughout the course of the study, Investigators are expected to monitor patients' PBC regimens and, if responsible for usual care, may adjust the regimen to achieve locally-appropriate treatment goals. These goals will be individualized, with the understanding that currently applicable PBC guidelines may vary across different geographic regions.

Ideally, patients should generally remain on the baseline PBC therapies throughout the course of the study, unless the baseline PBC therapy is no longer considered clinically appropriate by the Investigator. In addition, patients should be reminded to keep taking their blinded investigational product.

9.2.1. Drug Interactions

Bile acid sequestrants (BAS, including cholestyramine and its derivatives, colestipol, colesevelam, or other sequestrants) or aluminum hydroxide- or smectite-containing antacids should not be taken within 4 hours of taking investigational product (and UDCA if applicable), ie, BAS should be administered at minimum 4 hours before or 4 hours after investigational product administration.

OCA taken concomitantly with warfarin may result in decreased INR levels; therefore, INR should be monitored and the dosage of warfarin adjusted, as needed during treatment with OCA and after cessation of OCA, to maintain the target INR range.

The effect of OCA on drug metabolizing enzymes has been evaluated in both in vitro and clinical studies. The PK profile of caffeine, a sensitive CYP1A2 substrate probe, showed weak effect of OCA on CYP1A2. Based on these results, OCA may increase the exposure of narrow therapeutic index drugs that are substrates for CYP1A2, such as theophylline and tizanidine.

Information related to additional drug-drug interaction (DDI) studies is available in the current version of the IB. The aforementioned sections of the IB should be referred to during the course of the study, and are accessible to Investigators to help facilitate the assessment of potential DDIs with OCA that may be observed in study patients.

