5.3. Clinical Development of Obeticholic Acid

As of 28 October 2018, approximately 3470 subjects have received ≥ 1 dose of OCA. This estimation includes subjects from blinded ongoing studies. Of these 3470 subjects, 888 were healthy volunteers, 580 subjects had PBC, 72 subjects had PSC, 6 subjects had biliary atresia, 41 subjects had diabetes mellitus/ nonalcoholic fatty liver disease (NAFLD), 1914 subjects had NASH, and 33 subjects had portal hypertension due to alcoholic cirrhosis.

Overall, the pharmacokinetic (PK) profile of OCA is consistent with that expected of a bile acid. Phase 1 studies demonstrated that OCA is rapidly absorbed and extensively conjugated with

glycine and taurine to form glyco-OCA and tauro-OCA, respectively. OCA and its conjugates are primarily eliminated via biliary excretion, and plasma concentration time profiles demonstrated multiple peaking with prolonged exposure, indicative of enterohepatic circulation. Plasma concentrations of OCA and its conjugates spike shortly after meals, consistent with gall bladder emptying into the duodenum as expected of a bile acid.

The OCA clinical development PBC program was based on a wide range of studies in PBC patients and healthy volunteers. The clinical pharmacology studies supported the proposed dosing regimen: 10 mg fixed dose and a titration regimen starting at OCA 5 mg with titration to 10 mg based on clinical and biochemical response. The clinical program included a pivotal Phase 3 clinical study (747-301) and two Phase 2 clinical studies (747-201 and 747-202), which formed the primary basis of approval of OCA.

Study 747-201 (59 patients) evaluated 2 doses of OCA (10 mg and 50 mg) given as monotherapy versus placebo. Statistically significant and clinically relevant relative and absolute reductions from Baseline in alkaline phosphatase (ALP) were achieved with both doses of OCA versus placebo ($p < 0.0001$). Mean relative ALP reductions were 45% (OCA 10 mg) and 38% (OCA 50 mg) compared to an increase of 0.4% with placebo. Further, significant improvements in gamma-glutamyl transferase (GGT) and in conjugated bilirubin were observed with both doses compared with placebo ($p < 0.05$). OCA also resulted in decreased circulating alanine aminotransferase (ALT) and aspartate aminotransferase (AST) levels.

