9.2.2. Prohibited Medications

Commercial OCA therapy (if available) is prohibited while on investigational product, and if prescribed during the course of the study, the Investigator should be cognizant of the possibility of double dosing. Patients who initiate with commercial OCA therapy must discontinue investigational product and are expected to continue through the end of the study (see [Section 8.4.1](#)). Fibrin acid derivatives (ie, fibrates such as fenofibrate and bezafibrate) are also prohibited while on investigational product.

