12.1. Pharmacokinetic Blood Sampling

Serial and fasting PK assessments will be performed in all patients participating in the study.

[figure not shown]
At Day 1, and Weeks 6, 12, 18, 24, 30, 36, and 48, patients will provide fasted blood samples for measurement of OCA and its conjugates, glyco-OCA and tauro-OCA, and metabolite OCA glucuronide 30 minutes before administration of investigational product ([Table 8](#)). Patients will then receive a dose of investigational product with approximately 240 mL of water.

Week 6 Visit should occur 3, 4, or 5 days **after** the Week 6 dose (eg, if the Week 6 dose of investigational product is taken on a Sunday, the patient should come in for the Week 6 Visit between Wednesday and Friday [[Figure 3](#)]).

During the treatment period:

- Pharmacokinetic fasting samples will be obtained from all patients at Day 1, and Weeks 6, 12, 18, 24, 30, 36, and 48 prior to dose administration in accordance with [Figure 4](#).
- Serial PK assessments will be performed in all patients at Weeks 12, 18, 24, 30, and 48.

Figure 3: Week 6 Sampling Schedule

[figure not shown]

Week 6 Visit should be scheduled 3 to 5 days after the Week 6 OCA dose for collection of a single steady-state fasting PK sample

IP = investigational product; PK = pharmacokinetic

At Weeks 12, 18, 24, 30, and 48, serial PK blood samples will be obtained at 0.5, 0.75, 1, 1.5, 2, 2.5, 3, 4, 5, 6, 7, 8, 9, and 24 hours postdose (Figure 4) for all patients. The patient will be given the option to return to the clinic the following morning for the 24-hour postdose sample or samples can be obtained by a home health care designee. The home health care agency must be advised one week in advance of the appointment.

Figure 4: Pharmacokinetic Sampling Schedule

At meal timepoints, meals are consumed immediately after the collection of the PK sample

h = hour; IP = investigational product; PK = pharmacokinetic

Patients should not drink additional water for 1 hour after taking the dose of investigational product and will remain fasted until after the 1-hour sample is collected. A meal replacement drink will be provided following collection of the 1-, 4-, and 7-hour PK sample. The nutritional information of the meal replacement drink should be submitted to and approved by the Sponsor in advance. No other food or drink (water is permitted) will be allowed until after the 9-hour sample collection.

Table 8: Acceptable Windows for Pharmacokinetic Sample Collection

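### Section 9.2.1 lets bile acid sequestrants be taken inside the 0-24 h serial PK profile, with no provision for PK days and no required intake times

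*Protocol*

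**What the plan says.** - **Separation rule.** Section 9.2.1 covers bile acid sequestrants and aluminium hydroxide or smectite antacids, which must be kept 4 hours away from investigational product, and from UDCA where applicable. For sequestrants it adds: "BAS should be administered at minimum 4 hours before or 4 hours after investigational product administration". The rule is the same on every dosing day.
- **Other limits.** Section 9.2.2 prohibits commercial OCA and states that fibrates "are also prohibited while on investigational product". Sequestrants are not on that list, and Section 9.2 leaves non-prohibited medicines to the usual care provider.
- **Record.** Under Section 9.2, relevant information on concomitant medications "must be recorded in the source documents and eCRF, as well as any dose or dose regimen changes that occur during the study". No time of intake is asked for.
- **Serial PK.** Section 12.1: "Serial PK assessments will be performed in all patients at Weeks 12, 18, 24, 30, and 48". Samples are "obtained at 0.5, 0.75, 1, 1.5, 2, 2.5, 3, 4, 5, 6, 7, 8, 9, and 24 hours postdose". Meal drinks follow the 1, 4 and 7 h samples. Other food and drink, except water, is barred until the 9 h sample has been drawn. Sections 9.7.9 to 9.7.11 repeat these controls, and none of these sections mentions sequestrants in the PK-day instructions.
- **Pharmacology.** Section 5.1 calls OCA a modified bile acid. Section 5.3 describes biliary excretion, "multiple peaking with prolonged exposure, indicative of enterohepatic circulation", and concentration spikes shortly after meals.
- **PK Population.** Section 15.1 removes patients with major deviations that could affect exposure.

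**The concern.** The 4-hour gap keeps a sequestrant away from the tablet. It does not keep it away from OCA and its conjugates that return to the gut in bile later the same day. On serial PK days the drinks after the 4 h and 7 h samples prompt that return, and 4 h is also when a sequestrant becomes permitted. If a sequestrant binds recirculating OCA, the later part of the profile is lowered.

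A patient who takes a sequestrant at 4 h or later has followed the protocol. There is no deviation, so the PK Population definition does not remove the profile. The summaries could then mix the effect of hepatic impairment with the effect of the sequestrant, and the bias would understate exposure. An analysis plan can flag users from the medication record, but it cannot recover times of intake that were never collected.

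**Working it through.** The protocol gives no figure on this point to reproduce. The check is a reading of the rules together, plus arithmetic on the sampling schedule.

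**1. Is intake inside the profile compliant?** Section 9.2.1 permits it from 4 h after the dose. Section 9.2.2 does not prohibit it. The PK-day instructions in Sections 9.7.9 to 9.7.11 and 12.1 control fasting, water and meal drinks only. So it is compliant, and Section 15.1 keeps the profile.

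**2. How much of the profile can it touch?** Post-dose samples (Section 12.1): 0.5, 0.75, 1, 1.5, 2, 2.5, 3, 4, 5, 6, 7, 8, 9, 24 h, which is 14 samples.
- Later than 4 h: 5, 6, 7, 8, 9 and 24 h = 6 of 14 (43%). Time: (24 − 4)/24 = 20/24 = 83%.
- If the food and drink restriction is read as covering sequestrants, only the 24 h sample is later than 9 h = 1 of 14. Time: (24 − 9)/24 = 15/24 = 62.5%.
- This can recur at up to five serial visits per patient.

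These are ceilings on when intake is allowed. They do not measure how much exposure is affected.

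**3. What is recorded?** Use of a sequestrant and changes to its regimen are recorded, and concomitant medications are reviewed at each serial PK visit. Users are therefore identifiable. The protocol does not require the time that would place an intake before or after the dose and each sample.

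**4. How large could the effect be?** The protocol does not say. The following is an illustration with assumed inputs only. Let *s* be the share of AUC(0-24) after 4 h (50% to 85%), *r* the reduction of that part (10% to 50%), and *f* the share of OCA patients affected (10% to 50%).
- AUC ratio in a user: 1 − s·r. Low end: 1 − 0.5 × 0.1 = 0.95. High end: 1 − 0.85 × 0.5 = 0.575. The fall is 5% to 42.5%.
- Ratio of geometric means: (1 − s·r)^f. Low end: 0.95^0.1 = 0.995. High end: 0.575^0.5 = 0.758. The fall is about 0.5% to 24%.
- Small subgroup: at the planned minimum, CP-C patients number 0.20 × 50 = 10, so about 5 on OCA under 1:1 allocation. If PK were summarised by CP class, one user among five (f = 0.2) gives 0.95^0.2 = 0.990 to 0.575^0.2 = 0.895, a fall of about 1% to 10.5%.

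**5. Does the PK day alone matter?** No. Section 9.2.1 also permits sequestrants up to 4 h before the dose, and doses are a week apart or, on the twice-weekly schedule, at least 3 days apart. If binding of recirculating OCA matters, intake since the preceding dose can affect the predose sample as well.

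**The case against.** The strongest reply is that permitting background therapy is a defensible choice. Section 9.2 asks for stable concomitant medication before Day 1, and exposure is then measured under the permitted conditions of use. Presenting results with and without the affected profiles respects that choice.

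Other parts of the reply limit the point:
- A reader might infer that Sections 9.2.1 and 12.1 contradict each other. They do not. Both can be followed at once; what is missing is a statement of how the first applies on serial PK days.
- A reader might infer that the analyst has no means of separating affected patients. The medication record identifies users, so a summary with and without them is possible already. Only placement of intake relative to dose and samples is lost.
- A reader might take 83% as the share of exposure distorted. It assumes intake exactly at 4 h and counts hours. By samples it is a minority, and on the strict reading of the food and drink rule it is one sample. The UDCA clause may narrow the window further for patients taking UDCA.
- A reader might infer that distortion grows with dose, because Section 5.6 calls pruritus the main OCA-related event and dose dependent. The protocol does not say why patients take sequestrants, so this is not supported.
- Binding of recirculating OCA is an inference from Sections 5.1 and 5.3. The protocol does not state it, and for the antacids the support is weaker still.

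The reply that the analysis plan will deal with it fails on one count: intake times have to be collected during the trial.

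**Conclusion.** The point holds in a limited form. A patient who follows the protocol can take a sequestrant inside the serial PK profile and stay in the primary PK analysis, and nothing in the protocol requires the time of that intake. At most 6 of 14 post-dose samples and 20 of 24 hours are open to it, and possibly only the 24 h sample.

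Whether measured exposure is in fact lowered depends on two things the protocol does not give: how strongly sequestrants reduce recirculating OCA, and how many patients take them. The effect could be negligible if few do. The conclusion also assumes that the eCRF, which is not shown, does not already capture intake times; if it does, a cross-reference closes the point. It is worth correcting because PK is a primary objective in a small sample and the times cannot be collected afterwards.

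**What to change.** - Have the sponsor state in Sections 9.2.1 and 12.1 how the separation rule applies on serial PK days. What that rule should be is a clinical decision for the sponsor, and none is proposed here.
- At each serial PK visit, record the date and clock time of any sequestrant or binding-antacid intake from the preceding dose through the 24 h sample. A record limited to the PK day would miss intake before the dose and between doses.
- Flag profiles with such intake, and present the PK summaries with and without them.

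The cost is one added eCRF field, some recall burden on patients for the days since the preceding dose, and one repeated summary table. No change to sampling, visits or sample size is needed.

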Total Bilirubin	Closely monitor until normalization or stabilization. If values continue to increase relative to the baseline value, interrupt IP.	The patient may be rechallenged after a minimum of 30 days if fully resolved OR stable and approved by the Medical Monitor and Investigator. If laboratory values do not normalize, IP should not be restarted.
Baseline \leq ULN and 1.5 mg/dL increase from baseline Baseline $>$ ULN and 1.0 mg/dL increase from baseline		
INR^b	Closely monitor until normalization or stabilization. If values continue to increase relative to the baseline value, interrupt IP.	The patient may be rechallenged after a minimum of 30 days if fully resolved OR stable and approved by the Medical Monitor and Investigator. If laboratory values do not normalize, IP should not be restarted.
$>$ 0.3 increase from baseline		
\geq 2.0 unless due to vitamin K deficiency	Discontinue IP permanently	Continue to return for scheduled study visits for safety follow up. Monitor closely for clinical outcomes per protocol.
Laboratory Criteria for Monitoring Potential Hepatic Decompensation in the Presence of Clinical Symptoms		
Total bilirubin thresholds defined in Part B OR an INR increase from baseline of \geq 1.5 are observed in the presence of clinical symptoms of cholestatic hepatitis or hepatic encephalopathy ^c	Discontinue IP permanently	Continue to return for scheduled study visits for safety follow up. Monitor closely for clinical outcomes per protocol.

IP = investigational product

^a Sodium will be measured as an assessment of liver failure (hyponatremia).

^b Does not apply in patients on anti-coagulants.

^c Symptoms of cholestatic hepatitis includes dark urine and jaundice. Symptoms of hepatic encephalopathy may include lack of awareness, shortened attention span, lethargy, gross disorientation, or coma (unresponsive to verbal or noxious stimuli).

It should be noted that it is difficult to recognize every potential marker of hepatic or renal deterioration. There is no substitute for good medical judgment. Investigators will be reminded to be cautious and mindful in their evaluation of patients' symptoms, signs, and laboratory results. However, for example, a single abnormal laboratory analyte result may be artefactual; accordingly, Investigators will be allowed to implement an alternate follow-up procedure if considered appropriate based on their medical judgement, but only after documented agreement with the Sponsor's Medical Monitor.

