8.2. Patient Inclusion Criteria

1. A definite or probable diagnosis of PBC (consistent with American Association for the Study of Liver Diseases [AASLD] and European Association for the Study of the Liver [EASL] Practice Guidelines [Lindor 2009, EASL 2009]), defined as having ≥ 2 of the following 3 diagnostic factors:
 - History of elevated ALP levels for at least 6 months
 - Positive antimitochondrial antibody (AMA) titer or if AMA negative or low titer ($\leq 1:80$), PBC-specific antibodies (anti-GP210 and/or anti-SP100) and/or antibodies against the major M2 components (PDC-E2, 2-oxo-glutaric acid dehydrogenase complex)
 - Liver biopsy consistent with PBC (collected at any time prior to Screening)
2. Evidence of cirrhosis including at least one of the following:
 - Biopsy results consistent with PBC Stage 4
 - Liver stiffness as assessed by TE Value ≥ 16.9 kPa
 - Clinical evidence in the absence of acute liver failure consistent with cirrhosis including: gastroesophageal varices, ascites, radiological evidence of cirrhosis (nodular liver or enlargement of portal vein and splenomegaly)
 - Combined low platelet count ($< 140\,000/\text{mm}^3$) with:
 - persistent decrease in serum albumin, or
 - elevation in prothrombin time /INR (not due to antithrombotic agent use), or
 - elevated bilirubin ($2 \times$ ULN)
3. Satisfy the criteria of the modified CP classification for hepatic impairment during Screening:
 - Moderate: CP-B (Scores 7 to 9) or
 - Severe: CP-C (Scores 10 to 12)
4. MELD score of 6 to 24 at Screening
5. Age ≥ 18 years
6. Taking UDCA for at least 12 months (stable dose for ≥ 3 months) prior to Day 1, or unable to tolerate or unresponsive to UDCA (no UDCA for ≥ 3 months)
7. Contraception: Female patients must be postmenopausal, surgically sterile, or if premenopausal (and not surgically sterile), be prepared to use ≥ 1 effective method of contraception during the study and for 30 days after the end of treatment visit. Effective methods of contraception are considered to be those listed below:
 - Barrier method, ie, (a) condom (male or female) with spermicide **or** (b) diaphragm with spermicide; or

- Intrauterine device; or
 - Vasectomy (partner); or
 - Hormonal (eg, contraceptive pill, patch, intramuscular implant or injection); or
 - Abstinence, if in line with the preferred and usual lifestyle of the patient (where abstinence is defined as refraining from heterosexual intercourse)

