15.5. Efficacy Analyses

This study does not plan to test a formal hypothesis for any efficacy endpoint.

The endpoints of efficacy assessments are change in total and direct bilirubin, INR, creatinine, albumin, platelets, ALP, ALT, AST, and GGT from baseline to Week 48 (end of the study), change from baseline to Week 48 in CP score and components of the CP score, and change from baseline to Week 48 in MELD and components of the MELD score. Analyses of change from Baseline to Week 48 (end of study) will be modelled between treatment groups using ANCOVA model with change from Baseline as the dependent variable, treatment group and randomization stratification factor as fixed effects and the baseline value as a covariate. The same analysis will be carried out using percentage change from Baseline as the dependent variable.

Analyses of change from Baseline to Week 48 (end of study) will be modelled between treatment groups using ANCOVA model with change from Baseline as the dependent variable, treatment group and randomization stratification factor as fixed effects and the baseline value as a covariate. The same analysis will be carried out using percentage change from Baseline as the dependent variable.

Summary statistics of the laboratory values will be provided by treatment group. The results, change from Baseline, and percentage change from Baseline values, as well as estimates of least-square (LS) means, standard errors (StdErr), and 2-sided 95% CIs, will be presented by treatment group. Estimates of the mean difference between treatment groups, the StdErr of the difference, and 2-sided 95% CI of the difference will also be presented.

Risk Scores: Changes from baseline in the MELD score and in CP score, C4, FGF-19 and plasma bile acids will be summarized and analyzed using the Wilcoxon Rank Sum Test. The median differences and 95% CI of the median differences between treatment groups will be

constructed using Hodges-Lehmann estimate. If the median differences between treatments are not symmetrical around the median, the Sign Test may be used.

Shifts in MELD scores from Baseline will be reported by visit using the following categories: <10, 10 to <12, 12 to <13, 13 to <14, 14 to <15, and ≥ 15 .

CP class will be presented in shift tables showing the shift from baseline to each scheduled post-baseline visit by the count and percentage of patients within each shift classification.

Individual factors will be presented in a listing.

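### INR, MELD, Child-Pugh and MELD ≥15 are analysed with no provision for anticoagulated patients, although the protocol names an OCA–warfarin effect on INR

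*Protocol*

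**What the plan says.** **Anticoagulants are allowed.** Under Section 9.2, concomitant drugs other than the prohibited ones "will be used at the discretion of the usual care provider". Section 9.2.2 bars commercial OCA, and adds that fibrates "are also prohibited while on investigational product"; it names nothing else. No exclusion criterion in Section 8.3 mentions anticoagulants.

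**An interaction is named.** Section 9.2.1 says that "OCA taken concomitantly with warfarin may result in decreased INR levels", and continues that "INR should be monitored and the dosage of warfarin adjusted, as needed during treatment with OCA and after cessation of OCA", the aim being to hold the target range.

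**Anticoagulant-driven INR is set aside in two places.** Footnote b to the INR criteria of Table 3 (Section 7.4.2) reads "Does not apply in patients on anti-coagulants". The cirrhosis indicator that combines low platelets with a raised prothrombin time or INR (Sections 8.2 and 9.7.3) counts the latter only if "not due to antithrombotic agent use".

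**The endpoints carry no such provision.** Section 15.5 opens its list with "The endpoints of efficacy assessments are change in total and direct bilirubin, INR, creatinine, albumin, platelets, ALP, ALT, AST, and GGT", and goes on to Child-Pugh score and its components and to "change from baseline to Week 48 in MELD and components of the MELD score". INR is an input to MELD (Section 13.2.6) and one of the five Child-Pugh factors (Table 12). MELD ≥15, in patients with MELD ≤12 at baseline, is among the clinical endpoints of Section 15.6. Efficacy is summarised in the ITT Population (Section 15.1), that is, all randomised patients who were dosed.

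**The concern.** INR enters these endpoints as a marker of hepatic synthetic function. In a patient on warfarin it cannot serve as one. If the interaction is not fully corrected, INR falls because of the drug combination. If warfarin is adjusted to target, INR reports the target. In both cases the value says little about the liver.

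The two cases differ in their effect on the comparison. A corrected INR adds uninformative values to both arms. An uncorrected fall can occur only on OCA, and it lowers INR, MELD and possibly the Child-Pugh score, which reads as improvement on OCA.

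A second route concerns MELD ≥15. A patient who starts an anticoagulant during the study may cross the threshold without any hepatic deterioration, in either arm.

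MELD and Child-Pugh are the first two secondary objectives (Section 6.2), and Section 5.4.1 describes the data as a bridge to Study 747-302. The estimates will therefore be used even though nothing is formally tested.

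**Working it through.** The plan states no figure on this point, so there is none to reproduce. The steps below illustrate the size.

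**Inputs**
- About 50 patients randomised 1:1 (Section 15.2), hence 50 / 2 = 25 per arm.
- Child-Pugh points for INR (Table 12): below 1.7 scores 1, 1.7 to 2.3 scores 2, above 2.3 scores 3.
- INR term in MELD: 11.2 × ln(INR). This is an assumption. The formula is printed only as superseded text in the Version 3 change log (Appendix B); the current text names the inputs and a modification but gives no formula.
- INR values and the number of anticoagulated patients: not in the protocol, so assumed and varied.

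**Step 1. INR fall in one patient, liver unchanged.** Change in MELD = 11.2 × ln(INR after / INR before).

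| INR | Change in MELD | Change in Child-Pugh |
|---|---|---|
| 2.5 to 2.2 | 11.2 × ln(0.88) = −1.43 | 3 to 2 points: −1 |
| 2.5 to 2.0 | 11.2 × ln(0.80) = −2.50 | 3 to 2 points: −1 |
| 2.5 to 1.8 | 11.2 × ln(0.72) = −3.68 | 3 to 2 points: −1 |
| 2.5 to 1.6 | 11.2 × ln(0.64) = −5.00 | 3 to 1 points: −2 |

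**Step 2. Effect on the OCA mean.** Shift = (k / 25) × individual change, for k affected patients.
- INR 2.5 to 1.8: k = 1 gives −3.68 / 25 = −0.15; k = 2 gives −0.29.
- Over the range 2.5 to 2.2 through 2.5 to 1.6: k = 1 gives −0.06 to −0.20; k = 2 gives −0.11 to −0.40; k = 5 gives −0.29 to −1.0.

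**Step 3. Anticoagulant started on study.** INR 1.2 to 2.5 (assumed): 11.2 × ln(2.5 / 1.2) = +8.22 MELD points. A patient at MELD 7 would reach 7 + 8.22 = 15.22, so anyone with baseline MELD from 7 to 12 could cross 15. The arm mean moves by 8.22 / 25 = +0.33 for one patient and +0.66 for two.

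**Step 4. Size relative to the precision of the comparison.** For an assumed SD of MELD change of 2 to 4, the 95% CI half-width for the difference is 2.01 × SD × √(2/25), or 1.1 to 2.3 points. A shift of 0.15 is roughly 6% to 13% of that.

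**Step 5. Chance that the issue arises.** If 2%, 5% or 10% of patients were anticoagulated (assumed), the probability of at least one among 25 on OCA is 1 − 0.98^25 = 40%, 1 − 0.95^25 = 72%, or 1 − 0.90^25 = 93%.

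**The case against.** **This belongs in the SAP.** In part. Section 15.6 defers full details to the SAP, which was not available here and may contain a rule. Section 15.5 does not defer: it fixes the endpoints, model and covariates itself, and Section 15.1 fixes the population. Followed as written, they put these values into liver-function endpoints.

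**There is no contradiction.** This is fair as far as it goes. Footnote b limits a safety action, and the inclusion wording qualifies one of several cirrhosis indicators; neither governs endpoint analysis. They do show that the protocol expects anticoagulated patients and does not take their INR at face value.

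**Bias towards OCA is not established.** A reader might infer from Section 9.2.1 that the analysis is biased in favour of OCA. The documents do not support that. The text says only that INR may fall, concerns warfarin alone, and has warfarin adjusted to target. If adjustment is complete by Week 48, no systematic shift remains. For stable users, change from baseline with baseline as covariate handles part of the rest.

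**Adjudication protects MELD ≥15.** A reader might also infer that every anticoagulant start with a high MELD becomes an event. Sections 14.2.3 and 15.9 send suspected liver-related events to a blinded committee before analysis, so some or all may be removed. The charter is not shown, so neither outcome can be asserted. Adjudication does not reach the INR, MELD and Child-Pugh change analyses.

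**The effect is small and untested.** This stands. Section 15.5 plans no formal hypothesis test, and it also analyses MELD and Child-Pugh change by rank methods, which one outlying patient moves less than a mean.

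**Conclusion.** The point holds as a gap in the analysis of INR-based endpoints. Anticoagulants are permitted, the protocol names an INR effect that only the OCA arm can show, and it discounts anticoagulant-driven INR elsewhere, yet these patients enter the endpoints with no flag and no sensitivity analysis.

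The distortion favours OCA only where the fall in INR is not fully offset by warfarin adjustment. A spurious MELD ≥15 event is possible, not certain. The effect on an arm mean is probably small, about −0.15 MELD points per affected patient among 25, resting on an assumed INR fall from 2.5 to 1.8 and an assumed 11.2 × ln(INR) term. It could matter more for an individual Child-Pugh score or for a single event in arms of 25. The number of affected patients is not stated and may be zero. Type I error is not at issue.

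**What to change.** Keep the ITT analysis of all values as the main analysis. Add to Sections 15.5 and 15.6 a pre-specified sensitivity analysis of INR, MELD, the Child-Pugh prothrombin component and total, and MELD ≥15. It would exclude patients on an anticoagulant at baseline and values taken after an anticoagulant is started, flagged from the concomitant medication eCRF. Report the number affected by arm, and interpret INR, MELD and Child-Pugh changes in the light of it.

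Exclusion should not be the main analysis. Starting an anticoagulant is a post-randomisation event, so dropping later values may be informative, and Section 15.7 imputes nothing.

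Cost: a few sentences, one data flag, some extra analysis and slightly fewer values in the sensitivity analysis. Section 9.2 already requires the drugs and dose changes to be recorded. If no patient is anticoagulated, the two analyses coincide. No change to warfarin management is proposed.
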